5.16.4. Thrombotic Events

Potential Thrombotic Events (TEs) will be submitted by each Investigator for adjudication by the EAC using definitions pre-specified in the EAC Charter. The proportion of patients in the safety population who are adjudicated to have a TE by the independent EAC will be summarized. An exact 95% CI will be reported. Analysis will be performed for the safety patient population, by age category, sex, region, FXa inhibitor, bleeding type, andexanet dose, andexanet manufacturing process, medical history (i.e., atrial fibrillation (AF), Ischemic Stroke or Transient Ischemic Attack (CVA/TIA), Venous Thrombotic Event (VTE), or Cancer); and the type of TE (i.e., Ischemic Stroke (CVA), Myocardial Infarction (MI), Deep Vein Thrombosis (DVT), Pulmonary Embolism (PE), Arterial Systemic Embolism (ASE), and Transient Ischemic Attack (TIA). Also, the age, sex, FXa inhibitor, type of bleeding, previous history of TE, hospital length of stay and deaths for patients with and without thrombotic events will be compared.

An additional summary of possible TEs will be presented using a broader definition of TEs as recommended by FDA. See Section 4.6.8 for further details on the selection of events. The proportion of patients in the safety population who have a TE by this broader definition will be summarized. An exact 95% CI will be reported.

5.16.5. Antibodies to Andexanet, FX, FXa, HCP

To measure anti-andexanet antibodies (i.e., anti-drug antibodies [ADA]), samples are tested up to 3 times, each using a different electrochemiluminescence assay. The samples are tested sequentially so only samples that are positive in the previous assay are progressed to the next assay:

First, a screening assay is used to determine if there is antibody present in the sample. The result of this assay is either Detected or Not Detected.

Second, only if a sample has Detected antibody from the screening assay, a confirmatory assay is used to determine if the antibody is specific for the drug. The result of this assay is either Confirmed or Not Confirmed, and is only reported for samples for which the screening assay result was detected.

Third, if a sample has been confirmed to have ADA from the Confirmatory Assay, a titer assay is used to further determine the magnitude of the response. The titer result is a numeric value which is the reciprocal of the last dilution above the cut point that is positive.

The nature of any confirmed ADA will be further evaluated by a Neutralizing Antibody Activity assay. This assay uses the same Anti-fXa Activity assay for the PD samples, except that to each neutralizing antibody sample is added, *ex vivo*, a known amount of the anticoagulant (e.g., rivaroxaban), or anticoagulant *plus* andexanet. Each sample will have two test results listed as "Anticoagulant" and "Anticoagulant+andexanet." The neutralizing activity of the antibodies in the sample is inferred from the anti-fXa activity change from Pre-dose baseline to the later time points with the addition of anticoagulant vs. anticoagulant *plus* andexanet.

In data listings, the final result of the Anti-fXa activity assay will be reported as one of the following:

- · Not Detected, if the Screening Assay is negative
- · Not Confirmed, if the Screening Assay is positive but the Confirmatory Assay is negative
- Numeric, if the Screening Assay and Confirmatory Assay are both positive
- Neutralizing numeric, only for ADA, and only if the Screening Assay and Confirmatory Assay are both positive

In addition to the above, a modified Bethesda assay will be used to assess the potential presence of neutralizing antibodies against endogenous FX/FXa in all plasma samples from patients enrolled following the implementation of Protocol Amendment 4. The results will be listed by patient.

5.16.6. Clinical Laboratory Evaluations

Descriptive statistics will be calculated for the changes from baseline in hematology at 12 hours post and exanet dosing.

Each measurement will be classed as below, within, or above normal range, based on ranges supplied by the laboratory used. Shift tables in relation to the normal range from screening to end of study follow-up visit will be presented.

5.16.7. Vital and Hemodynamic Compromise Signs

Summary statistics for observed and changes from baseline in systolic and diastolic blood pressure, pulse rate, and heart rate will be tabulated at 1, 4, 8 and 12 hours post-dose.

24 hour vital sign data was only collected prior to issuing of protocol amendment 2 and therefore will be listed in Appendix but not formally summarized.

Threshold-based outlier analyses of post-dosing vital sign data will be presented based on the following definitions:

- Systolic blood pressure < 70 mmHg or > 180 mmHg
- Diastolic blood pressure < 40 mmHg or > 120 mmHg
- Pulse rate < 40 bpm or > 160 bpm
- Respiratory rate < 12 or > 40 breath/min

Details of whether the subjects showed any signs of post-baseline hemodynamic compromise will not be formally tabulated but listed in Appendix 16.2.

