5.3. Early Termination Visit

An early termination visit will be conducted if the patient is withdrawing from the study before the Follow-up Day 30 visit. Procedures at this visit will include the following:

- Record the reason for early termination.
- Record AEs since last study visit.
- Record use of concomitant medication since last study visit.
- Record dates of use of anticoagulant(s) on the anticoagulant CRF.
- Perform a final assessment of bleeding.
- Obtain a local laboratory Complete Blood Count (CBC).
- Collect central laboratory specimens for thrombin generation and antibodies (anti-andexanet, anti-fX, anti-fXa, and neutralizing antibodies).

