11.7.4. Laboratory Parameters

Clinical laboratory parameters including hematology, chemistry, and coagulation markers (e.g., anti-fXa activity and thrombin generation) will be summarized by time point.

Baseline values, the values at each subsequent visit, and changes from baseline will be summarized for each of the quantitative laboratory assessments.

Shift tables of chemistry, hematology, and coagulation markers will be used to summarize change from baseline to post-baseline time points.

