Appendix G: Examples of Minor Procedures Allowed

Appendix H: National Institutes of Health Stroke Scale (NIHSS)

Appendix I: Protocol Summary of Changes (Amendment 5 vs Amendment 6)

APPENDIX A. SCHEDULE OF ACTIVITIES

Study Day	1									2		3	$30^{[12]}$	
	-3:00	-00:15	00:00 to	EOB t (120 r		EI + 1 hr	EI + 4 hrs	EI + 8 hrs	EI +	EI + 18 hrs	EI + 24 hrs	EI + 48 hrs	EI + 72 hrs	
Study Hour and Time Window	to -00:01	to -00:01	EOB (15-30 min)	EOB +30 min	EI -30 min	+/- 30 min	+/- 30 min	+/- 90 min	+/- 1 hour	+/- 1 hour	+/- 1 hour	+/- 2 hour	+/- 6 hour	+7 d
Obtain Consent [1]	X													
Determine Eligibility	X													
Obtain Medical History [2]	X													
Obtain Prior Medications [2][13]	X													
Weight [3]	X													
Vital Signs (BP, HR, RR, temp)	X	X		X	X	X	X	X	X					
Local Labs: INR	X													
Local Labs: Chemistry & pregnancy test [4]	X													
Local Labs: CBC		X							X					
Critical Efficacy Central Labs: Anti-fXa activity unbound anticoagulant		[9] [14] X		[9] [14] X	[9] [14] X		X	X	X					
Critical Efficacy Central Labs: Thrombin Generation	X			X [11]	X [11]		X	X	X	X	X	X	X	X
Critical Immunogenicity Central Labs: Antibodies to andexanet, FX, FXa nAb (andexanet) nAb (FX/FXa)	X													X
Exploratory Efficacy Central Labs: TFPI Panel & ATIII	X				X		X	X	X		X	X	X	X

Study Day	1			1						2	3	3	30 ^[12]	
Study Hour and Time Window	-3:00 to -00:01	-00:15 to -00:01	00:00 to EOB (15-30 min)	EOB t (120 n EOB +30 min		EI + 1 hr +/- 30 min	EI + 4 hrs +/- 30 min	EI + 8 hrs +/- 90 min	EI + 12 hrs +/- 1 hour	EI + 18 hrs +/- 1 hour	EI + 24 hrs +/- 1 hour	EI + 48 hrs +/- 2 hour	EI + 72 hrs +/- 6 hour	+7 d
Administer and exanct bolus, immediately followed by an infusion			Bolus	Infus	ion									
Echocardiogram Pericardial Bleeds	X								X					
CT or MRI (e.g., ICH and intra-spinal) [5]	X [10]					X			X					X
Glasgow Coma score (ICH patients only)	X					X			X					X
Modified Rankin score (ICH patients only)	X					X			X					X
NIH Stroke Scale (ICH patients only) (Appendix H)		X				X			X					X
Record blood products and hemostatic treatments [6]		X												
Record bleeding-related diagnostic and therapeutic procedures [7]		X												
Record volume of colloid and crystalloid [6]			X											

Study Day		1					2	3	3	30 ^[12]				

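### The laboratory shift table in SAP 5.16.6 runs to the end-of-study visit, but the Amendment 6 schedule has no local laboratory draw after EI+12 h and no post-dose chemistry or INR

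*SAP*

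**What the plan says.** Clinical laboratory measurements are named in the safety objective (Protocol 2.4, SAP 2.4) and among the safety endpoints (Protocol 11.5.5).

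SAP 5.16.6 contains two planned analyses. The first is "Descriptive statistics will be calculated for the changes from baseline in hematology at 12 hours post" after dosing. The second classes each measurement as below, within or above the laboratory's normal range and then says: "Shift tables in relation to the normal range from screening to end of study follow-up visit will be presented". No analyte is named for the shift tables.

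Protocol 11.7.4 is broader. It says "Baseline values, the values at each subsequent visit, and changes from baseline will be summarized for each of the quantitative laboratory assessments", and also "Shift tables of chemistry, hematology, and coagulation markers will be used to summarize change from baseline to post-baseline time points". Its examples of coagulation markers are anti-fXa activity and thrombin generation.

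Appendix A is the only place where the sampling times are set. The relevant local laboratory rows are those beginning "Local Labs: INR", "Local Labs: Chemistry & pregnancy test [4" and "Local Labs: CBC". Outside the schedule, Protocol 5.3 requires one test at an early termination visit: "Obtain a local laboratory Complete Blood Count (CBC". Protocol 5.2 leaves laboratory tests at unscheduled visits to the investigator.

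**The concern.** A shift table cross-classifies each patient's baseline category against a follow-up category. If the follow-up sample is never scheduled, the table is either empty or filled by whoever happened to be tested. Here those would be patients who left the study early and patients tested for a clinical reason. A table built that way but labelled as a Safety Population result would have no clear denominator. An absence of shifts in it would say nothing about patients who followed the schedule.

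The same gap affects the chemistry change and shift summaries in Protocol 11.7.4. A reader of the plan would expect a post-dose comparison of creatinine, transaminases and bilirubin, because Protocol 10.2.3 lists these tests and gives routine safety as one of their purposes. The schedule does not supply one.

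**Working it through.** There is no sample size, power or error-rate figure to reproduce. The check is a count of schedule marks in Appendix A, set against the analyses promised.

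Appendix A has 14 time columns: two before the bolus, one for the bolus itself, two during the infusion, eight from EI+1 h to EI+72 h, and Day 30. Since 2 + 1 + 2 + 8 + 1 = 14, all columns are accounted for. Reading each row across gives:

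| Row | Pre-dose | Post-dose | Last scheduled draw | Day 30 |
|---|---|---|---|---|
| INR (local) | 1 | 0 | before bolus | none |
| Chemistry (local) | 1 | 0 | before bolus | none |
| CBC (local) | 1 | 1 | EI+12 h (± 1 h) | none |
| Anti-fXa activity (central) | 1 | 5 | EI+12 h | none |
| Thrombin generation (central) | 1 | 10 | Day 30 | yes |
| TFPI and ATIII (central) | 1 | 8 | Day 30 | yes |
| Antibodies (central) | 1 | 1 | Day 30 | yes |

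Draws during the infusion are counted as post-dose.

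Now set each promised analysis against these counts.

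1. SAP 5.16.6, hematology change at 12 hours. One pre-dose and one EI+12 h CBC are scheduled, so this can be done.
2. SAP 5.16.6, shift from screening to the end-of-study visit. Scheduled Day 30 draws are 0 for chemistry, 0 for INR and 0 for CBC, so 0 of 3 local panels can be tabulated for completers.
3. Protocol 11.7.4, chemistry at later visits, with change and shift. There are 0 scheduled post-dose draws, so neither a change nor a shift can be formed.
4. Protocol 11.7.4, hematology shift to a post-baseline time. This can be done, at EI+12 h only.
5. Protocol 11.7.4, coagulation markers. Anti-fXa activity can be summarized to EI+12 h and thrombin generation to Day 30. INR cannot be summarized after dosing.

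The distance between the last CBC and the intended endpoint is large. With a 30-minute bolus and a 2-hour infusion, EI+12 h falls at 0.5 + 2 + 12 = 14.5 h. Taking Day 30 as 30 × 24 = 720 h, the gap is 720 − 14.5 = 705.5 h, or about 29 days. The 12-hour CBC therefore cannot stand in for an end-of-study value.

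The unscheduled sources do not close the gap. The early termination visit adds a CBC but lists no chemistry or INR. Under Protocol 4.3, patients who discontinue are still to have the follow-up safety procedures unless they also withdraw consent for them, so this visit covers a particular kind of withdrawal.

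The rest of the SAP is consistent with the schedule rather than with the shift-table sentence. SAP 4.2.8 defines coagulation and biochemistry variables only before the bolus, as do Table 14.1.1.16 and Listing 16.2.4.5. The post-dose outputs for local tests are hemoglobin change at 12 hours (Table 14.3.4.3) and a hematology listing (Listing 16.2.8.4). The table list contains no laboratory shift table, although it is described as a sample that will not be updated. SAP 5.17.2 does not record any narrowing of Protocol 11.7.4.

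**The case against.** The strongest reply is that this is a wording mismatch with limited consequences. The SAP sentence names no analyte, the only group named in its section is hematology, and the SAP elsewhere treats chemistry and INR as baseline data. The chemistry promise sits in Protocol section 11, which describes itself as a summary to be detailed in the SAP. Protocol 3.5 places laboratory safety monitoring in the first 12 hours. Clinically significant laboratory worsening is reportable as an adverse event (Protocol 9.1), and adverse events are collected through Day 30 (Protocol 9.6). Nothing here touches the primary endpoints, adjudicated thrombotic events or mortality.

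Most of that stands, and it limits the point. It does not remove it: the SAP sentence still names a visit with no scheduled local test, and Protocol 11.7.4 still names chemistry explicitly. Adverse event reporting can reveal a laboratory change, but only where someone chose to test, so it does not replace a scheduled comparison.

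Three stronger readings are tempting, and the documents do not support them.

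- A reader might infer that the laboratory safety objective cannot be answered. Hematology and anti-fXa activity to 12 h and thrombin generation to Day 30 are scheduled and can be analyzed.
- A reader might infer that none of the 477 patients had a planned post-dose chemistry or INR sample. Appendix A is the Amendment 6 schedule, and SAP 5.17.1 says patients entered under successive amendments. Other assessments did change: Amendment 1 removed a 24-hour time point and Amendment 2 shortened follow-up from 45 to 30 days. The earlier laboratory schedules are not in these documents.
- A reader might infer that every shift table in Protocol 11.7.4 should go. Its own examples of coagulation markers have post-dose samples, so deleting those tables would discard a feasible analysis.

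**Conclusion.** The point holds in a bounded form. Under the Amendment 6 schedule, the shift table in SAP 5.16.6 has no scheduled end-of-study data for any of the three local panels, and the chemistry change and shift summaries in Protocol 11.7.4 have no scheduled post-dose data at all. Per completing patient, scheduled post-dose draws are 0 for chemistry, 0 for INR and 1 for CBC, the last at EI+12 h. Any end-of-study entries would come from early withdrawals or discretionary testing.

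This is a stated analysis that the design cannot deliver, and it should be corrected before reporting. It affects part of the laboratory safety evaluation and no efficacy conclusion. The conclusion assumes that Appendix A governed sampling. If patients enrolled under earlier amendments had later chemistry, INR or CBC draws, the zeros would not apply to them. The number of such patients cannot be found from these documents.

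**What to change.** In SAP 5.16.6:

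- Define the hematology shift table as last pre-dose CBC to EI+12 h, for the analytes in Protocol 10.2.3 (hemoglobin, hematocrit, white cells, platelets).
- Report chemistry and INR at baseline only, and record this in SAP 5.17.2 as a change from Protocol 11.7.4.
- Keep the post-baseline summaries of anti-fXa activity and thrombin generation at their scheduled times.
- Put early-termination and unscheduled laboratory results in a listing, not in a summary table.

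In the study report, state that post-dose chemistry and INR were not systematically collected, so changes in them are captured only through adverse event reporting.

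Extra sampling is not a remedy, because the SAP analyzes 477 locked patients. The cost is a few sentences of SAP and report text. No analysis with scheduled data is lost. The downside is that the stated laboratory safety evaluation becomes narrower than the protocol implies.

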5.16.8. Post Dose Procedures Performed to Evaluate Bleeding

Number of patients who had the evaluative diagnostic, therapeutic and imaging procedures used after the first and exanet dose along with the procedures used will be tabulated Change to Original Protocol and Planned Statistical Analysis

5.17. Changes to the Original Protocol and Planned Statistical Analysis

5.17.1. Protocol Amendments

No patients were enrolled under the original protocol (dated 30 July 2014). For the current dataset, all patients were enrolled under one of four protocol amendments: Protocol Amendment 1, dated 30 January 2015; Protocol Amendment 2 dated 07 May 2015; Protocol Amendment 3, dated 27 October 2015 (a Netherlands-specific amendment); Protocol Amendment 4, dated 06 January 2017, Protocol Amendment 5, dated 02 July 2018, and Protocol Amendment 6, dated 30 November 2018.

Changes in the protocol that impacted the conduct of the study included the following:

5.17.1.1. Amendment 1 (30 January 2015)

- Modified the primary efficacy objective and primary efficacy endpoint to include changes in anti-fXa activity. The two primary efficacy endpoints will be tested sequentially, with the proportion achieving hemostatic efficacy tested only if the change in anti-fXa activity is first demonstrated.
- Modified the secondary efficacy objective and secondary efficacy endpoint to assess the
 relationship between the two primary efficacy endpoints: to evaluate the relationship
 between change from baseline to the evaluation period in anti-fXa activity and
 effective hemostasis.

- Eliminated the original Study Day 1, 24-hour study data point and updated time points to Day 1, 8-hour and Day 1, 12-hour data points.
- Clarified the requirements, inclusion, and exclusion criteria regarding acute major bleeding.
- Changed the definition of history prior to screening from 1 month to 2 weeks.
- Modified follow-up to include rescue therapy for patients with a poor or no response.
- Provided specific detail on the measurement of closed bleeds to document hemostatic control.
- Increased the number of sites allowed in North America and Europe from 60 to 120.

5.17.1.2. Amendment 2 (07 May 2015)

- Modified the duration of safety follow up from 45 to 30 days to align follow-up period with standard clinical practice for ICH recovery timelines.
- Clarified that (visible) bleeding must be overt to qualify for inclusion in this trial.
- Clarified that ICH bleeds can be diagnosed and assessed with either CT or MRI.
- Included edoxaban as one of the factor Xa inhibitors that could qualify a patient for this
 trial. Also, clarified that the list of factor Xa inhibitors being studied in this study is
 restricted to apixaban, edoxaban, rivaroxaban, and enoxaparin.
- Clarified that patients who are scheduled for surgery to occur within the first 12 hours after receiving and examet should not be enrolled in this study.
- Clarified the blood and blood-related products allowed as well as the time frames allowed.
- Increased the size of allowable hematoma volume from 30 cc to 60 cc to enable the
 patient population to be more representative of what might be expected in the
 clinical setting.
- Shortened and/or consolidated the restrictions around duration of prior exposure to medications to within 7 days of andexanet treatment, based on expected duration of effect.
- Provided specificity around rating of hemostatic efficacy for different subtypes of ICH.

5.17.1.3. Amendment 3 (27 October 2015)

Amendment 3 was a country-specific amendment for the Netherlands. The content of Amendment 3 was largely identical to that of Amendment 2, with the exception that the discretion to enroll patients who were unable to provide informed consent for themselves, either by proxy or emergency consent, was dependent on local laws and regulations.

5.17.1.4. Amendment 4 (06 January 2017)

- Increased sample size from 250 patients to 350 patients.
- Enriched patient population for ICH; ensured a minimum of 110 efficacy evaluable ICH patients, including 50 patients at high risk for hematoma expansion.
- Added a requirement for a reasonable expectation that a patient would be treated with andexanet within 2 hours after a baseline scan (ICH patients only).
- Excluded patients with visible, intra-articular, and musculoskeletal bleeding.
- Excluded patients for whom the Investigator believed that the hemoglobin would drop below 8 g/dL after volume resuscitation.
- Changed threshold of efficacy evaluability for enoxaparin patients from 0.5 IU/mL to 0.25 IU/mL.
- Added clinical criteria for re-bleeding and guidance for re-dosing of andexanet in the event of re-bleeding.
- Added re-bleeding, TFPI, ATIII, anti-IIa activity, GCS, mRS, and NIHSS as exploratory efficacy endpoints.
- Converted thrombin generation from a safety endpoint to an efficacy endpoint, and mortality from an efficacy endpoint to a safety endpoint.
- Updated and exanet dosing recommendations.

5.17.1.5. Amendment 5 (02 July 2018)

- To established lower anti-fXa activity threshold for patients taking edoxaban to reflect contemporary understanding of risks and benefits of edoxaban.
- Efficacy evaluable patients was re-defined as follows: All patients must have a central laboratory-determined anti-fXa activity ≥ 75 ng/mL for patients receiving apixaban and rivaroxaban, ≥ 40 ng/mL for patients receiving edoxaban, and ≥ 0.25 IU/mL for patients receiving enoxaparin. All other criteria stayed the same.
- Exclusion criteria #5 was updated as follows: The patient has a recent history (within 2 weeks) of a diagnosed Thrombotic Event (TE) as follows: Venous Thromboembolism (VTE; e.g., deep venous thrombosis, pulmonary embolism, cerebral venous thrombosis), myocardial infarction (including an isolated troponin elevation), disseminated intravascular coagulation (DIC), cerebral vascular accident, transient ischemic attack, unstable angina pectoris hospitalization, or severe peripheral vascular disease within 2 weeks prior to Screening (see Appendix E for DIC scoring algorithm).
- Clarified definition of re-bleeding to be consistent throughout protocol.
- Update and clarification for IP return and destruction.

5.17.1.6. Amendment 6 (30 November 2018).

- Corrected an error in the Synopsis and updated for accuracy and to align with the protocol body.
- Clarified that adverse events and survival was to be followed through the study.
- Updated to simplify the description of the study periods related to safety monitoring.
- As a surrogate for elevated anti-fXa activity, the eligibility criteria restrict enrollment to
 patients who received their last dose of FXa inhibitor within 18 hours, if the timing is
 known. (If the timing of the last dose of FXa inhibitor is unknown, the andexanet bolus
 must begin as soon as possible–following signing of the ICF and completion of
 pretreatment procedures—but no later than 3 hours following signing of the ICF.)
- Updated for clarity exclusion criteria 4.2.
- Updated the andexanet dosing to reflect accurate ranges of < 30 mg (low dose) and ≥ 30 mg (high dose) for andexanet dosing in patients receiving edoxaban.

